7.2 Descriptive Analysis

A descriptive analysis of baseline characteristics will be conducted comparing HEPLISAV-B and comparator vaccine recipients. Variables described in Section 6.3 will be extracted from electronic health records. Categorical variables will be presented as absolute numbers and percentages with p-values for the χ^2 test. Continuous variables such as age in years will be presented as the mean with standard deviation and interquartile ranges, with p-values for the two-sample t-test or Wilcoxon rank-sum test, as appropriate. The rates of occurrence of first AMI event during the study period among HEPLISAV-B recipients and comparator vaccine recipients will be described.

A detailed flowchart of the AMI outcomes by study cluster, including total number of cases identified through the databases, reasons for exclusion, number of cases attended outside of KPSC, number of definite / probable / unable to determine (eg, medical records not available) / not a case (eg, medical records did not substantiate a clinical diagnosis), and number of AMI by type will be provided with the final analysis report.

7.3 Primary Analysis

For the final analysis of the primary objective, we will use a non-inferiority framework to test the null hypothesis of increased risk of Type 1 AMI among HEPLISAV-B recipients versus comparator vaccine recipients. Based on anticipated number of confirmed events, the study will have approximately 87% power to exclude a hazard ratio of 2.0 or greater (Section 7.9), testing the hypothesis: H_0 : $HR \ge 2$, H_a : HR < 2.

The rates of occurrence of first Type 1 AMI event during the study period among HEPLISAV-B recipients and comparator vaccine recipients will be compared using a Cox proportional hazards regression model employing inverse probability of treatment weighting (IPTW)^[33]. The IPTW provides an assessment of the closeness of match in the weighted analysis across all variables, providing a sense of the degree of control of imbalance between the vaccine exposure groups. Two tables will be created comparing the cohort of HEPLISAV-B recipients to the cohort of recipients of the comparator vaccine. The first table will be unweighted, showing the true distribution of recipient characteristics. The second table will be weighted by the inverse probability of treatment as estimated by a propensity score model. Standardized difference scores will be used to assess whether balance of covariates is achieved between the cohorts. These 2 tables will show the effectiveness of the weighting at reducing effective differences between the cohorts.

The primary analysis will be conducted on confirmed Type 1 AMIs. Variables to consider in the propensity model are listed in Section 6.3. The primary exposure will be vaccine group

(HEPLISAV-B vs. comparator vaccine), and the outcome will be confirmed AMI. Clustering by medical center will be considered through random effects variables representing medical center. Censoring events will include end of study, disenrollment from Kaiser Foundation Health Plan (allowing for a 31-day gap in membership), and death from causes other than AMI. A hazard ratio of AMI for HEPLISAV-B versus the comparator vaccine, adjusted for potential confounding factors, and associated 95% confidence interval will be reported.

7.4 Sensitivity Analyses

7.4.1 Sensitivity Analyses Using Alternative Statistical Methods

Sensitivity analyses will be performed using alternative approaches (besides IPTW). These will include: (1) a Cox proportional hazards model adjusted for and/or stratified by propensity score; and (2) a traditional multivariable Cox proportional hazards regression model. The use of a propensity score as a stratifying or control variable permits the control of potential confounding variables with a single summary variable, reserving degrees of freedom to test the primary association. The traditional multivariable Cox model allows examination of the effect of each potential confounder on the estimate and control for many factors simultaneously. Variables to be considered in the propensity model include those considered in the primary IPTW analysis. The traditional Cox model will be adjusted for demographics and comorbidities (Section 6.3). Adjusted hazard ratios of AMI for HEPLISAV-B versus the comparator vaccine and associated 95% confidence intervals will be reported.

7.4.2 Interpretation of Sensitivity Analyses

It is expected that the primary analysis and the sensitivity analyses would yield similar results. Should they be discrepant, the DMC may suggest additional analyses to better understand the reason for the differences and to determine the most likely correct analysis and interpretation.

7.5 Secondary Analysis

A secondary analysis will be conducted comparing the rates of occurrence of Type 1 unconfirmed AMI in the principal discharge diagnosis position in the HEPLISAV-B group to a historical group of patients from the HEPLISAV-B medical centers who received comparator vaccine in 2016. Patients ages 18 years and older will be included in the historical comparison group if they were vaccinated with non-dialysis formulation hepatitis B vaccine from 01 January 2016 to 31 December 2016 in KPSC family practice and internal medicine departments included in the HEPLISAV-B group in the post-licensure safety study and were KPSC members on the day of vaccination. Patients receiving chronic dialysis in the 3 months prior to hepatitis B vaccination will be excluded. In the unlikely event that someone receives vaccine in both time periods, they will only be included in the HEPLISAV-B cohort. Relative risk will be estimated using a Cox proportional hazards regression model with IPTW to adjust for differences in the populations, as described in Section 6.3.

If this comparison shows a significantly elevated risk for the HEPLISAV-B group, additional analyses will be performed in order to further investigate the elevated risk. We will graphically investigate the timing of the events relative to vaccination. We will perform sensitivity analyses by first dose vs. subsequent dose of hepatitis B vaccine and by concomitant vaccination status.

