4.4 Study Period

The study will begin with administration of the first dose of HEPLISAV-B and is contingent upon ACIP and RIPC recommendation of HEPLISAV-B. The study vaccination period will occur until 25,000 patients have received at least 1 dose of HEPLISAV-B, expected to take approximately 10.5 months based on historical vaccination trends. Each patient will be followed until the earliest of disenrollment from KPSC (not due to death and allowing for a 31-day gap in membership), death from any cause, or the end of the 13-month follow-up period after the index dose given during the vaccination period.

Table 4-1:Adult Hepatitis B Vaccine Recipients: Active Member at First Dose
Date, 2015 by Target (HEPLISAV-B) and Comparator Medical
Centers

	8 Comparator	7 Target	Total
	Medical Centers	Medical Centers	
N	47,964	45,766	93,730
Age (years)			
Mean (SD)	49.1 (10.83)	49.0 (10.90)	49.1 (10.86)
Sex	n (%)	n (%)	n (%)
Female	23,229 (48.43)	22,400 (48.94)	45,629 (48.68)
Male	24,735 (51.57)	23,366 (51.06)	48,101 (51.32)
Race/Ethnicity	n (%)	n (%)	n (%)
Asian	4043 (8.43)	5810 (12.7)	9853 (10.51)
Black	4027 (8.4)	4742 (10.36)	8769 (9.36)
Multiple	242 (0.5)	190 (0.42)	432 (0.46)
Native Am/Alaskan	152 (0.32)	127 (0.28)	279 (0.3)
Others	340 (0.71)	432 (0.94)	772 (0.82)
Pacific Islander	728 (1.52)	691 (1.51)	1419 (1.51)
Unknown	1107 (2.31)	829 (1.81)	1936 (2.07)
White	14,482 (30.19)	7914 (17.29)	22,396 (23.89)
Hispanic	22,843 (47.63)	25,031 (54.69)	47,874 (51.08)
Had type 2 diabetes history prior to the first dose	n (%)	n (%)	n (%)
No	9851 (20.54)	10,094 (22.06)	19,945 (21.28)
Yes	38,113 (79.46)	35,672 (77.94)	73,785 (78.72)
Had AMI history between 01/01/2010 to first dose date	n (%)	n (%)	n (%)
No	47,359 (98.74)	45,260 (98.89)	92,619 (98.81)
Yes	605 (1.26)	506 (1.11)	1111 (1.19)
Had hospitalized AMI in 12 months after first dose date	n (%)	n (%)	n (%)
No	47,891 (99.85)	45,713 (99.88)	93,604 (99.87)
Yes	73 (0.15)	53 (0.12)	126 (0.13)

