5.2 Hepatitis B Vaccination of Adults With Diabetes

In 2014, KPSC implemented an electronic alert and reminder embedded in electronic health records prompting providers to order hepatitis B vaccine for previously unvaccinated adults with diabetes ^[25]. This resulted in a significant increase in completion of the 3-dose series among adults with diabetes, although coverage with all 3 doses remained low (<30%). In 2015, adults with diabetes comprised approximately 79% of the 93,730 KPSC members who received a dose of hepatitis B vaccine (Table 4-1).

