5.3 Study Inclusion and Exclusion Criteria

5.3.1 Inclusion Criteria

- 1. Received at least one dose of hepatitis B vaccine (either HEPLISAV-B in HEPLISAV-B arm, or non-dialysis formulation hepatitis B comparator vaccine in comparator arm) at KPSC during study vaccination period.
- 2. Enrolled as a KPSC member at time of hepatitis B vaccination during the study vaccination period.
- 3. Age 18 years or older at time of hepatitis B vaccination during study vaccination period.
- 4. Received hepatitis B vaccine at KPSC family practice or internal medicine departments, or in urgent care or nurse clinics affiliated with those departments.

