6.0 STUDY METHODS

6.1 Exposure of Interest

The exposure of interest for this study is the index dose of hepatitis B vaccine (Section 4.2).

Hepatitis B vaccine exposure will be assigned at the cluster level. At target medical centers, providers in family practice and internal medicine departments will only be able to order HEPLISAV-B for hepatitis B vaccination of adult patients not on dialysis. Patients receiving an index dose of HEPLISAV-B in family practice or internal medicine departments will be included in the HEPLISAV-B cohort.

At non-target medical centers, providers in family practice or internal medicine departments will only be able to order a hepatitis B comparator vaccine other than HEPLISAV-B. Only patients receiving an index dose of comparator vaccine in family practice or internal medicine departments will be included in the comparator cohort. In recent years at KPSC, Engerix-B has been used for routine vaccination, while Recombivax-HB (Dialysis Formulation) has been used for dialysis patients. As dialysis patients are not included in this study, the comparator is expected to be Engerix-B.

Adults vaccinated with one or more doses of comparator hepatitis B vaccine prior to study initiation who did not complete the full 3-dose regimen may be given HEPLISAV-B if they

receive care at a HEPLISAV-B target medical center. These patients will be included in the primary analysis, while exploratory analyses will seek to identify differential outcomes between these patients and those who received their first dose of hepatitis B vaccine during the study period (Section 7.6).

While providers are advised to follow ACIP and RIPC recommendations, decisions regarding the appropriateness of administering a hepatitis B vaccination and the vaccination schedule will be determined by the healthcare providers and patients. Vaccine exposure will be identified retrospectively from the electronic health records, including vaccine, dose, manufacturer, and lot number entered at the time of vaccination. Data on vaccine exposure will be checked using quality control procedures described in Section 8.2 below.

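### Section 7.5 drops 2016 controls who later receive HEPLISAV-B, so control membership depends on surviving after the index dose; the likely bias is small and tends to favour HEPLISAV-B

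*Protocol*

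**What the plan says.** Protocol Section 7.5 (Secondary Analysis) compares unconfirmed Type 1 AMI in the principal discharge position between HEPLISAV-B recipients and a "historical group of patients from the HEPLISAV-B medical centers who received comparator vaccine in 2016". Eligible controls are adults "vaccinated with non-dialysis formulation hepatitis B vaccine from 01 January 2016 to 31 December 2016" in the same departments, who were health plan members on that day and not on chronic dialysis. The analysis is a Cox model with inverse probability of treatment weighting (IPTW).

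On people who qualify for both groups, Section 7.5 states: "In the unlikely event that someone receives vaccine in both time periods, they will only be included in the HEPLISAV-B cohort".

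Two other places bear on this:

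- Section 5.3.1 requires a HEPLISAV-B recipient to be "Enrolled as a KPSC member at time of hepatitis B vaccination during the study vaccination period".
- Section 6.1 gives the route by which a 2016 recipient can enter the HEPLISAV-B cohort: at target centers, adults with earlier comparator doses "who did not complete the full 3-dose regimen may be given HEPLISAV-B". Section 7.6 plans an exploratory analysis of subsequent-dose recipients.

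The protocol does not state how many people are expected in both groups.

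**The concern.** A cohort should be defined by what is known at its index date. Here, whether a person vaccinated in 2016 stays in the control group depends on what happens to them afterwards. To be removed, they must be alive, be a member at the later date and be vaccinated again. Anyone who died of AMI in the 2016 window can never be removed. If those removed had fewer AMIs than the 2016 cohort as a whole, their removal takes out more person-time than events. The historical rate then rises and the hazard ratio (HEPLISAV-B over historical) falls.

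IPTW uses characteristics measured before the index dose, so it does not undo selection on survival after it. The section states no sensitivity analysis of the rule.

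This is a safety comparison, and the likely error runs toward the study vaccine. Section 7.5 also makes further work on event timing, dose order and concomitant vaccination conditional on a significantly raised risk in this comparison. A downward shift makes that trigger slightly less likely to fire.

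**Working it through.** **The plan's own figures.** The protocol gives no figure for the historical comparison. Its primary planning figures reproduce. Expected events are 50,000 × 1.02 × 0.0015 = 76.5, against 78 stated. Power with 78 events to exclude a hazard ratio of 2.0 is Φ(√78 × ln 2 / 2 − 1.96) = 0.8645, against 0.865 in Table 7-1. The 1.5 per 1,000 person-years and 1.02 person-years per recipient are therefore usable for scale.

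**Formula.** Let q be the share of control person-time removed, and k the AMI rate of removed persons relative to the whole 2016 cohort with rate r. The remaining rate is r(1 − qk)/(1 − q), so

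observed HR = true HR × (1 − q)/(1 − qk).

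The factor is below 1 when k < 1, equals 1 when k = 1 and exceeds 1 when k > 1. Neither q nor k is in the protocol; both are assumed below.

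| q | k = 0 | k = 0.5 | k = 0.85 | k = 1.2 |
|---|---|---|---|---|
| 1% | 0.990 | 0.995 | 0.999 | 1.002 |
| 5% | 0.950 | 0.974 | 0.992 | 1.011 |
| 10% | 0.900 | 0.947 | 0.984 | 1.023 |
| 20% | 0.800 | 0.889 | 0.964 | 1.053 |

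**Which k does the mechanism support?** A simulated 2016 cohort used 1.5 AMIs per 1,000 person-years, 13 months of follow-up, 10% loss and a true hazard ratio of 1. It gave these factors for an overlap of 5%, 10% and 20%:

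| Assumption about AMI patients | 5% | 10% | 20% |
|---|---|---|---|
| none died or left | 1.003 | 1.006 | 1.014 |
| 10% died or left before the study period | 0.997 | 0.995 | 0.986 |
| 20% died or left | 0.991 | 0.981 | 0.959 |
| 20% died or left, survivors half as likely to be revaccinated | 0.969 | 0.938 | 0.868 |
| no AMI patient ever revaccinated (limit) | 0.947 | 0.895 | 0.789 |

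The third row corresponds to k of about 0.84. The first row lies just above 1 because, in that setting, no AMI patient leaves while 10% of the others do.

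**Plausible overlap.** Take 45,766 target-center recipients in 2015 (Table 4-1), a 15% decline to 2016 and a 90% share in the study departments (Section 7.9 assumptions). The 2016 control is then about 45,766 × 0.85 × 0.90 ≈ 35,000. If 5% of the 25,000 HEPLISAV-B recipients had a 2016 dose, q = 1,250/35,000 ≈ 3.6%; if 10%, about 7.1%. An overlap of 20% would mean 7,000 people, or 28% of the HEPLISAV-B cohort.

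**Against sampling error.** Expected events are 25,000 × 1.02 × 0.0015 ≈ 38 and 35,000 × 1.02 × 0.0015 ≈ 54, so SE(log HR) ≈ √(1/38 + 1/54) ≈ 0.21. A factor of 0.98 is a log shift of 0.020, about a tenth of a standard error. A factor of 0.96 is about a fifth.

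**Do the windows overlap?** The last 2016 index date is 31 December 2016, so the last 13-month window ends by 31 January 2018. Section 7.1 places the first interim about 12 months after study start, with its report due by 31 August 2019. With the 3-month data lag of Section 6.4, that points to a start around the middle of 2018. The start date is implied, not stated.

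**The case against.** The strongest reply is that the effect is too small to matter. Patients with a non-fatal AMI can be revaccinated and removed too, so removed persons are not all event-free. Section 4.1 describes alerts and a policy of vaccinating at any visit. AMI survivors who attend more often could therefore be revaccinated more often, which would push k to 1 or above and cancel or reverse the shift. The analysis is secondary, uses unconfirmed events and leaves the primary comparison untouched. All of this stands, and it limits the size. It does not justify defining controls by a later event when the alternative costs almost nothing.

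Several stronger readings are tempting but are not supported:

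- *Calling overlap improbable contradicts Sections 6.1 and 7.6.* Those sections show only that overlap can happen. They give no frequency and are not specific to 2016 recipients.
- *Three-dose coverage below 30% (Section 5.2) means most 2016 recipients could be removed.* That figure is coverage among adults with diabetes, not non-completion among people who started in 2016.
- *The hazard ratio could be cut by 10 to 20%.* That needs a large overlap and almost no revaccination of AMI survivors, which goes well beyond death or departure.
- *The rule decides whether any dose-order analysis is run.* Section 7.6 plans first-dose and subsequent-dose comparisons unconditionally, though against the concurrent comparator.
- *Calendar time, or the 2015 difference in AMI risk between center groups in Table 4-1, adds to this point.* The first applies to any historical control and the second to the concurrent comparison. Neither bears on the overlap rule.

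**Conclusion.** The point holds, as a minor one. The rule in Section 7.5 selects controls on survival, continued enrollment and revaccination after the 2016 index dose, and baseline weighting does not repair that. The hazard ratio is pushed down whenever removed persons had a below-average AMI rate. That is the likely direction, because a fatal AMI is impossible among them, but it is not certain.

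From death or departure alone the shift is probably about 1 to 4% for an overlap of 5 to 20%, assuming 20% of AMI patients had died or left. It is about 0.3 to 1.4% if only 10% had. It would reach 3 to 13% only if AMI survivors were also half as likely to be revaccinated. Overlap, attrition and revaccination are all assumptions, because the protocol gives none of them. A reader might infer that the primary non-inferiority result is at risk; it is not, since the rule applies only to the historical comparison.

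**What to change.** In Section 7.5, replace the overlap rule as follows:

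- Define the 2016 group by information available up to the 2016 index dose only.
- Keep every eligible 2016 recipient for their own 13-month window, whatever vaccine they receive later.
- Let a person contribute to both cohorts, with variance clustered on person.
- Report the number of people in both groups and confirm from the actual start date that their two windows do not overlap.

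The cost is a change of wording, a person identifier in the variance estimate and one count in the report. No new data are needed. If the existing rule is to be kept for any reason, run it as a sensitivity analysis beside the corrected one.

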required, with the second dose 1 month after the first; this schedule may reduce barriers and improve vaccination coverage of adults. Furthermore, HEPLISAV-B has demonstrated significantly greater and earlier seroprotection compared to Engerix-B, including in persons with diabetes.

Safety data from adults who received at least 1 dose of HEPLISAV-B in pre-licensure clinical trials have demonstrated a similar safety profile when compared to the licensed hepatitis B vaccine, Engerix-B. Adverse events were generally mild and infrequent. The rates of serious adverse events and events leading to study discontinuations were also similar between HEPLISAV-B and Engerix-B except for a numerical imbalance in events coded with the Medical Dictionary for Regulatory Activities (MedDRA) preferred term of *acute myocardial infarction* (AMI) in a single trial, HBV-23 (HEPLISAV-B: 0.25% [n = 14]; Engerix-B: 0.04% [n = 1]). The myocardial infarctions occurred in subjects in whom such events would be expected based on their high prevalence of baseline cardiovascular risk factors, occurred randomly with no temporal relationship to time of vaccine administration, occurred at lower than expected incidence rates, and were not related to a persistent inflammatory state or an autoimmune condition ^[6]. Based on the totality of the data, the imbalance was most likely due to random variation in the small number of events reported but did not unequivocally prove no increase in risk. However, this risk of acute myocardial infarction will be monitored in the post-marketing observational surveillance study described in this protocol.

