6.2 Outcome of Interest

The outcome of interest is the first occurrence of AMI during the 13-month follow-up period for each patient.

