7.9 Power Analyses

Approximately 50,000 patients (HEPLISAV-B: 25,000; another hepatitis B vaccine: approximately 25,000) will be included in the study and the accrual is assumed to be uniform during a period of approximately 10.5 months. Each patient will be followed for up to 13 months after their first dose of HEPLISAV-B or comparator vaccine administered during the study vaccination period. A 10% loss to follow-up during the study with a uniform loss rate is assumed. Assuming no difference in the risk of AMI between the two groups, we anticipate approximately 41 events at 12 months, 68 events at 18 months, and 78 events at the end of study if the event rate is 1.5/1000 person-years. In the first interim analysis, the study will have approximately 83% power to detect a hazard ratio \geq 2.5 and 60% power to detect a HR \geq 2.0, and in the second interim analysis the study will have 81% power to detect a HR \geq 2.0. In the final analysis, the study will have approximately 87% power to exclude HR \geq 2.0. The anticipated number of events based on other event rates and the power for a non-inferiority test based on other non-inferiority margins for the final analysis is presented in Table 7-1.

Time, Months	Event rate per 1000 person- years	# Events	Power, HR = 2.0 alpha = 0.025	Power, HR = 2.5 alpha = 0.025	Power, HR = 3.0 alpha = 0.025	Power, HR = 3.5 alpha = 0.025	Power, HR = 4.0 alpha = 0.025
9	1.0	16	0.277	0.44	0.583	0.696	0.782
	1.5	23	0.388	0.601	0.757	0.858	0.918
	2.0	31	0.490	0.725	0.866	0.938	0.972
12	1.0	27	0.442	0.669	0.820	0.906	0.952
	1.5	41	0.603	0.836	0.941	0.980	0.994
	2.0	55	0.728	0.924	0.982	0.996	0.999
18	1.0	45	0.644	0.869	0.959	0.988	0.997
	1.5	68	0.814	0.965	0.995	0.999	1.000
	2.0	90	0.909	0.992	0.999	1.000	1.000
24	1.0	52	0.705	0.911	0.977	0.995	0.999
	1.5	78	0.865	0.982	0.998	1.000	1.000
	2.0	104	0.942	0.997	1.000	1.000	1.000

Table 7-1:	Power for a Non-inferiority Test to Reject a Hazard Ratio in a Cox
	Proportional Hazards Model

Assumptions:

- Final HEPLISAV-B medical centers will be the same 7 as initially planned or will result in the same number of vaccine recipients in each arm
- Only doses given in family practice and internal medicine will be included (90% of all adult hepatitis B vaccine doses)
- Essentially all doses in HEPLISAV-B medical centers in family practice and internal medicine will be HEPLISAV-B

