- Accrual of both HEPLISAV-B and comparator vaccine is roughly evenly distributed through the year (primarily affects number of person-years of follow up at interim analysis)
- Total doses given annually during the study period will be ~30% fewer than the number given in 2015 (~15% decline seen from 2015 to 2016, lesser decline observed subsequently)
- 10% lost to follow-up rate during 13-month follow-up, assuming a uniform loss rate, giving an average of 1.02 person-years per recipient at the final analysis

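### The protocol's only look at when AMIs occur after vaccination depends on a significantly raised 13-month average hazard ratio in the historical comparison, a condition that a short early risk would usually not meet

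*Protocol*

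**What the plan says.** Section 6.2 defines the outcome as the "first occurrence of AMI during the 13-month follow-up period for each patient". The interim analyses (7.1), the primary analysis (7.3) and the sensitivity analyses (7.4.1) use Cox models that report a hazard ratio over follow-up. The exploratory analyses (7.6) split by vaccination history, not by time since the dose.

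Timing appears only in 7.5. That section compares HEPLISAV-B recipients with 2016 recipients of the comparator at the same centers, on unconfirmed Type 1 AMI in the principal discharge position: "Relative risk will be estimated using a Cox proportional hazards regression model with IPTW to adjust for differences in the populations". It then sets a condition, "If this comparison shows a significantly elevated risk for the HEPLISAV-B group, additional analyses will be performed", and the first item under it is: "We will graphically investigate the timing of the events relative to vaccination".

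The Introduction (2.0) says of the AMIs in HBV-23 that they "occurred randomly with no temporal relationship to time of vaccine administration", as part of the argument that the 14 versus 1 imbalance was probably chance. The same paragraph concedes that the data did not settle the matter.

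**The concern.** The condition tests the quantity in which a short post-dose risk is hardest to see. If the excess is confined to a few weeks, most of the 13 months contributes person-time at a hazard ratio of 1 and pulls the average towards 1. The timing graph would then tend to be skipped in just those studies where it would be informative.

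The condition is also attached to the historical comparison of unconfirmed events. A raised estimate in the primary concurrent comparison of confirmed events leads to no specified timing analysis.

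The study could report that a hazard ratio of 2.0 is excluded and leave open whether risk was raised soon after vaccination. Since the protocol uses absence of a temporal pattern as evidence about HBV-23, readers will want the same question answered in a cohort of about 50,000.

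**Working it through.** **1. The plan's own figure.** Section 7.9 gives about 87% power to exclude a hazard ratio of 2.0 with 78 events at one-sided 0.025. With 1:1 allocation, power = Φ(√78 × 0.5 × ln 2 − 1.96) = 0.865, which is the Table 7-1 entry. Events: 50,000 × 1.02 × 1.5/1000 = 76.5, close to the stated 78.

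**2. Inputs for the condition in 7.5.**
- Follow-up (7.9): "Each patient will be followed for up to 13 months after their first dose of HEPLISAV-B or comparator vaccine".
- Person-time (7.9): "giving an average of 1.02 person-years per recipient at the final analysis".
- HEPLISAV-B group: 25,000 at 1.5 per 1000 person-years, so 25,000 × 1.02 × 0.0015 = 38.25 events without excess risk.
- Historical group: the protocol gives no number, so this is an assumption. Low value 25,000 (38.25 events). High value from Table 4-1 and the 7.9 assumptions: 45,766 × 0.85 × 0.90 ≈ 35,000 (53.6 events).
- Further assumptions: two-sided 0.05 (7.5 names no level), constant baseline hazard, the 1.5/1000 rate for unconfirmed events, and no variance inflation from weighting. Inflation would lower the probabilities below.

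**3. Dilution.** Average HR = 1 + (HR in window − 1) × f, where f is the window's share of person-time. With 10% uniform loss, f is 0.080 for 30 days and 0.158 for 60 days.

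**4. Probability that the condition is met.** SE = √(1/historical events + 1/HEPLISAV-B events); probability = Φ(ln(average HR)/SE − 1.96).

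| Assumed early risk | Average HR | HEPLISAV-B events | Condition met (25,000 to 35,000 historical) |
|---|---|---|---|
| 3-fold, 30 days | 1.16 | 44.3 | 10-11% |
| 5-fold, 30 days | 1.32 | 50.4 | 25-29% |
| 3-fold, 60 days | 1.32 | 50.4 | 25-29% |
| 5-fold, 60 days | 1.63 | 62.5 | 67-75% |

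Example, 5-fold over 30 days with 25,000 historical patients: SE = √(1/38.25 + 1/50.4) = 0.214; ln 1.318 / 0.214 − 1.96 = −0.67; Φ = 0.25. The observed average HR must reach about 1.46 (35,000 historical) to 1.51 (25,000) for significance.

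**5. What the primary test would conclude.** Take 39 comparator events (half of 78), a risk confined to month 1 of 13, and SE = √(1/39 + 1/(39 × HR)).
- 3-fold: average HR = (3 + 12)/13 = 1.15; SE = 0.219; P(upper limit below 2) = Φ[(ln 2 − ln 1.154)/0.219 − 1.96] = 0.71.
- 5-fold: average HR = (5 + 12)/13 = 1.31; SE = 0.213; the same probability is 0.51.

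With a 30-day window and 38.25 events the figures are 0.70 and 0.49.

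**6. What an unconditional early comparison could show.** With 25,000 per group, about 3.0 comparator events are expected in 30 days and 6.1 in 60 days. Exact conditional binomial test, one-sided 0.025:

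| Window | HR 2 | HR 3 | HR 4 | HR 5 |
|---|---|---|---|---|
| 30 days | 9% | 31% | 58% | 80% |
| 60 days | 22% | 64% | 90% | 98% |

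For a 3-fold risk over 60 days this is 64%, against 25-29% for meeting the condition in 7.5.

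**The case against.** The strongest reply is that 13-month risk is the declared estimand. If the 13-month hazard ratio really is 1.31, excluding 2.0 is the right answer, and the early-risk scenarios are assumptions that nothing in the protocol supports; the Introduction in fact reports no temporal pattern. This stands as a defence of the primary test. It does not defend the condition on the timing analysis, and the protocol itself says the earlier data were inconclusive.

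A second reply is that event-time plots and window-specific hazard ratios belong in the statistical analysis plan, which may contain them. Nothing in 7.5 forbids further timing work, so one cannot say that no one will look. The objection here is narrower: the protocol does specify a timing analysis, and attaches it to a condition that works badly.

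Three stronger readings are tempting and are not supported.
- A reader might infer that the timing analysis would never be reached. A 5-fold risk over 60 days meets the condition in about two thirds to three quarters of studies.
- A reader might infer that a raised interim estimate has no consequence. Section 7.1 requires immediate FDA notification and a comparison of confirmed AMIs if the crude hazard ratio is at least 2.5 with a lower 95% limit above 1. What is absent is a timing analysis.
- A reader might take the graph to be a screen for early risk that fails at its task. Section 7.5 presents it as follow-up of an elevation already found. The consequence is that the protocol specifies no screen for early risk.

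**Conclusion.** The point holds in this limited form. The only timing analysis in the protocol is graphical, uses unconfirmed events, and depends on a significant 13-month average against historical patients. For a short or moderate early risk the condition would usually not be met: it would be missed in about nine studies in ten for a 3-fold 30-day risk, and in roughly three in four (71-75%) for a 5-fold one. In about 71% or 51% of studies with such a one-month risk, the final analysis would exclude 2.0 over 13 months and leave the early period unreported.

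The percentages rest on the assumed windows, risk sizes, historical group size and significance level. The direction does not: any risk confined to a short window is diluted in the average. The primary hypothesis test is not invalid. This is a weakness in the supporting analyses that should be corrected.

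**What to change.** Remove the condition in 7.5 for the timing analysis. In the final analysis, report for confirmed Type 1 AMI against the concurrent comparator, whatever the overall result:
- an event-timing plot by vaccine group;
- hazard ratios with 95% confidence intervals for a prespecified early window after the index dose (for example days 0-60, which spans the intended two HEPLISAV-B doses one month apart) and for the remaining follow-up.

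Label these as supportive estimates with no effect on the primary test. No additional early-window display is needed at the interims.

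The cost is a few lines of text and one more model on data already held. The downside is imprecision: a 30-day comparison has only about 31% power at a hazard ratio of 3 and 9% at 2, so the text should say that an unremarkable early estimate does not rule out a modest early risk. A window anchored on the index dose also does not follow later doses, in particular those of a comparator series given over 6 months, and the report should state this.
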